5.4 Follow-up

To determine any carry-over effects in the present study, a follow-up assessment will be conducted 8 weeks (± 7 days) post cessation of treatment. As treatment status will be blinded, all participants will be re-administered all outcome measures and laboratory tests (excluding pregnancy test) at follow-up. While no existing data exist on the carry-over effects of Lovastatin, in patients with cancer who were given high dosages of Lovastatin (2-45mg/kg/day)

approximately 30 days after the cessation of Lovastatin, cholesterol levels returned back to normal levels (Thibault et al., 1996).

All study personnel that have responsibility for direct participant related activities will be intensively trained in the relevant specific procedures before contact with participants, which includes providing informed consent/assent, family/child interviews, the administration and scoring of tests, maintenance of confidentiality, data collection and handling, and procedures for handling difficulties that might arise during the study. All study personnel who have direct contact with study participants or their data, will sign a confidentiality form, indicating their understanding of appropriate procedures for maintaining participant confidentiality. Doctoral-level neuropsychology staff and physicians will provide the relevant training and ongoing supervision of all study personnel.

6.0 Pharmaceutical Information

6.1 Pharmacokinetics

Lovastatin is one of the first-generation statins and therefore has a large body of safety and pharmacokinetic data from clinical trials and general use for hyperlipidemia (Corsini, et al., 1995a).

1. It is a lactone that is readily hydrolyzed in vivo to the corresponding b-hydroxyacid, a potent inhibitor of HMG-CoA reductase. Inhibition of HMG-CoA reductase is the basis for an assay in pharmacokinetic studies of the b-hydroxyacid metabolites (active inhibitors) and, following base hydrolysis, active plus latent inhibitors (total inhibitors) in plasma following administration of Lovastatin;
2. Following an oral dose of ¹⁴C-labeled Lovastatin in men, 10% of the dose was excreted in urine and 83% in feces. Plasma concentrations peaked at two hours and declined rapidly to about 10% of peak by 24 hours post dose;
3. Lovastatin is highly bound (>95%) to human plasma proteins. Animal studies demonstrated that Lovastatin crossed the blood brain and placental barriers;
4. The major active metabolites present in human plasma are the b-hydroxyacid of Lovastatin, its 6^{''}-hydroxy derivative, and two additional metabolites. Peak plasma concentrations of both active and total inhibitors were obtained within two to four hours of dose administration;
5. The recommended dose in children 10 to 17 years old is 10-40 mg/day (Merck & Co., Inc, 2007);
6. It is metabolized in the liver by the cytochrome P450 isoenzyme CYP3A4, with less than 10% being excreted renally (Kantola, Kivisto & Neuvonen, 1998);
7. With a once a day dose regimen, plasma concentrations of total inhibitors over a dosing interval achieved a steady state between the second and third days of therapy and were about 1.5 times those following a single dose (Vree, Dammers, Ulc, Horkovics-Kovats, Ryska et al., 2003). When Lovastatin is given under fasting conditions, plasma concentrations of total inhibitors were on average about two thirds those found when

Lovastatin was administered immediately after a standard test meal (Hsu, Spinler & Johnson, 1995; (Merck & Co., Inc, 2007).

6.2 Drug Company/Supply/Distribution

Based on an estimate from Eminent Corporation, funds included in the budget will be used to purchase Lovastatin and its matching placebo and distribute Med Kits to participating sites. Eminent Corporation will also be responsible for study medication reconciliation and shipping.

6.3 Procedures/Recommendations for Drug Supply and Distribution

Lovastatin and its matching placebo will be obtained and distributed to participating sites by a subcontractor to the Operations Center. A 20mg tablet of Lovastatin or an identical tablet (placebo) will be provided for each participant. Medications, including the placebo, will be provided to the participants free of charge. Participants will be instructed to return all unused medications as well as empty bottles at each clinic visit. All unused medicine will be disposed of properly at each individual site.

Lovastatin is administered orally. The bioavailability of the tablet increases under the influence of a meal. Based on these findings, it is advised to take the tablets immediately after a meal. One dose per day after dinner time will be instructed to parents, since evening doses are more effective than the same dose given in the morning (Merck & Co., Inc, 2007). Lovastatin is a substrate for cytochrome P450 isoform 3A4 (CYP3A4). Grapefruit juice contains one or more components that inhibit CYP3A4 and can increase the dose concentration. Participants will be instructed to avoid the consumption of grapefruit juice during the treatment. A complete list of drug interactions/contraindications will be described to parents and participants.

Compliance will be monitored by recording the number of pills dispensed to families from the pharmacy and then comparing that to the number of pills that are returned at each monthly visit. Participants will be asked to return all unused pills at each visit. A pill diary will also be maintained by each participant and reviewed at each follow-up visit to ensure compliance with the medication.

6.4 Drug Dosage and Possible Interactions

The selection of the maximum dose of Lovastatin to be used in this study, 40 mg/day, is based on the tolerability of the drug when used for heFH and the results of the Phase I study examining safety and tolerability of Lovastatin in children with NF1 (Acosta et al., submitted). Participants will commence at 20 mg/day for two weeks and escalate to the 40 mg/day dose in week 3.

Approximately 40% of children with NF1 are diagnosed with comorbid ADHD, many of whom are treated with psychostimulant medication such as methylphenidate and/or dextroamphetamines. In order to minimize recruitment bias and ensure recruitment targets are met, patients taking methylphenidate and/or dextroamphetamines will be eligible for this study.

The predominant metabolic pathway of methylphenidate is de-esterification to form pharmacologically inactive d- or l-ritalinic acid (Patrick et al 1987). Metabolism of methylphenidate when used by oral administration undergoes a stereoselective clearance to ritalinic acid (CES1A1 is the major enzyme responsible) before entering systemic circulation (Sun et al, 2004). Methylphenidate does not use the microsomal cythochrome P450 in the liver for its metabolism (Sun et al 2004; Patrick et al 1987). Dextroamphetamines are metabolized by the cythochrome P450 in liver. However the isoenzyme responsible for its metabolism is the CYP2D6 (Adderall Medication Guide, Shire, Nov. 2010). Instead, lovastatin is metabolized by the CYP3A4 (Ritalin® Medication Guide, Novartis, 2010). There are not described interactions or competitive mechanism between dextroamphetamines and lovastatin.

Although limited by a small sample size, results of the Phase I study provide some evidence for the inclusion of patients on stimulant medication (Acosta et al., submitted). A total of 23 patients with NF1 (10-17 years of age) completed 12 weeks of treatment with Lovastatin. Nine patients had a diagnosis of ADHD and five of these patients were taking a stable dose of stimulant medication during the course of the study. Calculation of Reliable Change Index for individuals indicated significant improvements on both verbal and nonverbal memory measures in approximately 40% of participants regardless of whether they were off or on methylphenidate.

The list of psychotropic medications is quite extensive. As many psychotropic medications may interact with the metabolism of Lovastatin, e.g. Fluoxetine, patients taking psychotropic medications other than stimulant medications will be excluded from the study. Also, participants on other medications to control behavior (including Straterra) and anticonvulsants will not be eligible to participate in the study as these medications are known to affect cognition and learning and, thus, confound the results of the study. However, these participants may be eligible if they cease medication for at least 30 days prior to screening and remain off these medications for the duration of the study. Importantly, all participants must still demonstrate impairment on either of the primary outcome measures at the screening assessment and satisfy all other inclusion criteria to be enrolled in the study.

6.5 Toxicity and Adverse Event Monitoring

6.5.1 Lovastatin Side Effects

Lovastatin has been shown to be safe and effective in a pediatric population for treatment of familial heFH with minimal toxicity. The FDA has approved it for treatment in children and it is believed to be safe to extend to other potential uses. Side effects reported have been considered reversible once the medication has been discontinued. The most frequent side effects of Lovastatin are described below by systems. Presentation is less common in children than in adults, and includes:

Muscular: Muscle pain, tenderness, weakness, increase of CPK, cramps, rhabdomyolysis (rare)

Hematologic: Thrombocytopenia

Gastrointestinal: Abdominal pain, flatulence, diarrhea, constipation

Hepatic: Transient elevation in serum transaminases

Dermatologic: Rash (rare)

Constitutional: Fatigue, asthenia, flu-like symptoms, headache, dizziness, insomnia

6.5.2 Frequencies of side effects

The frequencies of adverse events are ranked according to the following: Very Common ($>1/10$), Common ($\geq 1/100$, $<1/10$), Uncommon ($\geq 1/1,000$, $<1/100$), Rare ($\geq 1/10,000$, $<1/1,000$), and Very Rare ($<1/10,000$).

Common $>1\%$ and $<10\%$ (less than 1 person in every 10 but more than 1 person in every 100): Gastrointestinal disorders: constipation, dyspepsia

Uncommon 0.1% to 1% (less than 1 person in every 100 but more than 1 person in every 1,000): Skin and subcutaneous tissue disorders: itching; elevated transaminases.

Rare 0.01% to 0.1% (less than 1 person in every 1,000):

- Eye disorders: blurred vision.
- Gastrointestinal disorders: abdominal pain, diarrhea, dry mouth, flatulence, nausea, vomiting.
- General disorders and administration site conditions: weakness.
- Hepatic disorders: yellowing of the skin and eyes (cholestatic jaundice), hepatitis.
- Metabolism and nutrition disorders: loss of appetite.
- Musculoskeletal, connective tissue and bone disorders: muscle weakness (myopathy), tenderness and muscle pain, muscle cramps. Participants will be told to promptly report any unexplained muscle pain, tenderness or weakness. If myopathy is diagnosed or suspected, then Lovastatin therapy will be immediately discontinued.
- Nervous system disorders: dizziness, absence of the sense of taste, headache, tingling sensation, tingling and numbness of the feet and legs.
- Psychiatric disorders: insomnia, psychic disturbances including anxiety, sleep disorders.
- Skin and subcutaneous tissue disorders: alopecia, spotted or diffuse redness of the skin including Stevens - Johnson syndrome, redness and swelling of the skin, shedding of the skin.
- An apparent hypersensitivity syndrome has been reported rarely which has included one or more of the following features: anaphylaxis, angioedema, lupus-like syndrome, polymyalgia rheumatica, dermatomyositis, vasculitis, thrombocytopenia, leukopenia, eosinophilia, hemolytic anemia, positive anti-nuclear antibodies, erythrocyte sedimentation rate increase, arthritis, arthralgia, urticaria, asthenia, photosensitivity, fever, flushing, chills, dyspnea and malaise, and other liver function test abnormalities including elevated alkaline phosphatase and bilirubin; increase in serum CPK levels.

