5.2.3 Off-Study Criteria (Note: See Section 6.6 for modifications for toxicity information)

A participant will be taken off the study for the following reasons:

- The participant refuses further treatments and/or wishes to withdraw from the study;
- For participants concurrently taking stimulant medications (methylphenidate and/or dextroamphetamines), they will be withdrawn from the study if they stop or change the dose or type of stimulant medication before their final study visit;
- It is deemed in the best interest of the participant to stop the study by the research team;
- Serious protocol violation or non-compliance as determined by the principal investigator or research team;
- The development of significant drug toxicity, such as recurrent grade 3 or 4 toxicity after dose reduction; and/or persistent grade ≥ 2 toxicity for >10 days without administration of the drug;
- The development of a concurrent serious medical condition that might preclude or contraindicate the administration of Lovastatin;
- Death.

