6.6 Modifications for Toxicity

Participants who experience grade 2 toxicity related to Lovastatin will have Lovastatin withheld until the toxicity resolves (grade ≤ 1) and then restarted at the same dose level. If the grade 2 toxicity recurs, the dose will be withheld again until the toxicity resolves (grade ≤ 1) and then reduced to 50% of the dose. If the grade 2 toxicity recurs, the participant will be taken off the protocol. The participant will be evaluated by the principal investigator.

Participants who experience grade 3 or 4 toxicity related to Lovastatin will have their dose withheld. If the toxicity returns to grade ≤ 1 within 10 days, the participant may resume Lovastatin at a dose reduced by 50%. If the toxicity persists at grade ≥ 2 for >10 days without administration of Lovastatin or the grade 3 or 4 toxicity recurs at the lower dose, the participant will be removed from the study.

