Headache	none	mild pain not interfering with function	moderate pain: pain or analgesics interfering with function, but not interfering with activities of daily living	severe pain: pain or analgesics severely interfering with activities of daily living	disabling
GASTRO-INTESTINAL					
Abdominal pain or cramping	none	mild pain not interfering with function	moderate pain: pain or analgesics interfering with function, but not interfering with activities of	severe pain: pain or analgesics severely interfering with activities of daily living	disabling

			daily living		
Constipation	none	requiring stool softener or dietary modification	requiring laxatives	requiring manual evacuation or enema	obstruction or toxic megacolon
Diarrhea participants without colostomy:	none	increase of <4 stools/day over pretreatment	increase of 4-6 stools/day, or nocturnal stools	increase of >7 stools/day or incontinence; or need for parenteral support for dehydration	physiologic consequences requiring intensive care; or hemodynamic collapse
Flatulence	none	mild	moderate	-	-
HEPATIC					
AST	WNL	>ULN - 2.5 x ULN	>2.5 - 5.0 x ULN	>5.0 - 20.0 x ULN	>20.0 x ULN
ALT	WNL	>ULN - 2.5 x ULN	>2.5 - 5.0 x ULN	>5.0 - 20.0 x ULN	>20.0 x ULN
Bilirubin	WNL	>ULN - 1.5 x ULN	>1.5 - 3.0 x ULN	>3.0 - 10.0 x ULN	>10.0 x ULN
MUSCLE					
CPK (creatine phosphokinase)	WNL	>ULN - 2.5 x ULN	>2.5 - 5 x ULN	>5 - 10 x ULN	>10 x ULN
Muscle weakness (not due to neuropathy)	normal	asymptomatic with weakness on physical exam	symptomatic and interfering with function, but not interfering with activities of daily living	symptomatic and interfering with activities of daily living	bedridden or disabling
Myositis (inflammation/damage of muscle) Also consider CPK. Note: Myositis implies muscle damage (i.e., elevated CPK).	none	mild pain, not interfering with function	pain interfering with function, but not interfering with activities of daily living	pain interfering with function and interfering with activities of daily living	bedridden or disabling
Myalgia (muscle pain)	none	mild pain not interfering with function	moderate pain: pain or analgesics interfering with function, but not interfering with activities of daily living	severe pain: pain or analgesics severely interfering with activities of daily living	Disabling

B. TIMETABLE

As outlined in the statement of work, the general timetable of this project is as follows:

0 – 12 weeks: Initiation of the study and subject recruitment

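### For a drug-related event that is also suspected myopathy, protocol sections 6.5.2 and 6.6 agree on stopping Lovastatin but conflict on restarting it, and no precedence is stated

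*Protocol*

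**What the plan says.** **Section 6.5.2 (Frequencies of side effects).** Within the list of rare effects, the musculoskeletal entry reads "muscle weakness (myopathy), tenderness and muscle pain, muscle cramps". Families are to report unexplained muscle symptoms promptly. The rule follows: "If myopathy is diagnosed or suspected, then Lovastatin therapy will be immediately discontinued". It carries no grade threshold, no causality condition and no restart provision.

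**Section 6.6 (Modifications for Toxicity).** The rule for grade 2 begins: "Participants who experience grade 2 toxicity related to Lovastatin will have Lovastatin withheld until the toxicity resolves", meaning grade 1 or lower, "and then restarted at the same dose level". After one recurrence the drug is withheld again and the dose is then halved. After a further recurrence the child comes off protocol. For grade 3 or 4 the drug is withheld, and then: "If the toxicity returns to grade ≤ 1 within 10 days, the participant may resume Lovastatin at a dose reduced by 50" per cent. Removal follows if the toxicity recurs at the lower dose, or "If the toxicity persists at grade ≥ 2 for >10 days without administration of Lovastatin".

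**Section 6.11 (Risks and Protection from Risks).** Adverse events related to study medication are to be managed as 6.6 sets out. Muscle events are not excepted.

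**Appendix 7.** CPK, muscle weakness, myositis and myalgia each have their own graded row. Section 6.8 introduces this appendix as the severity grading for effects related to Lovastatin.

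**Section 5.2.3 (Off-Study Criteria).** Its heading points to 6.6. Its examples of significant drug toxicity include persistent grade 2 or higher "toxicity for >10 days without administration of the drug". Myopathy is not named.

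**The concern.** Section 6.5.2 puts a stopping rule for one named condition inside a list of side-effect frequencies. The section a site would consult for dose changes, 6.6, does not mention that rule, and its general wording takes in the same events. A site working from 6.6 and a site working from 6.5.2 could both believe they were complying and yet differ on whether a child with suspected myopathy goes back on drug.

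The first stake is the consistent handling of a safety event in children. Section 4.1 acknowledges a lack of preliminary safety data at ages 8 and 9. The second is the tolerability objective (2.2.2): exposure, dose-reduction counts and treatment-stop counts would depend partly on which section a site had read. There may also be a smaller effect on outcome timing. Under 5.3 a child withdrawn early is tested at that point if at least four weeks have passed since baseline, whereas a child who restarts would ordinarily be tested at week 16.

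**Working it through.** The plan gives no figure to reproduce. The check is to apply each rule to the same event.

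**Step 1: do the rules overlap?** Section 6.6 does not name muscle toxicity. The overlap rests on three things: 6.6 covers any related toxicity of grade 2 or above, Appendix 7 grades muscle weakness and myositis, and 6.11 sends related events to 6.6 without exception. Because 6.5.2 glosses muscle weakness as myopathy, related grade 2 weakness falls under 6.6 and, where myopathy is suspected, under 6.5.2 as well.

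**Step 2: apply both rules to a related event that is also suspected myopathy.**

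| Event | 6.5.2 | 6.6 | Result |
|---|---|---|---|
| Below grade 2 | Stop, no restart given | Silent | No conflict |
| Grade 2, first episode | Stop, no restart given | Withhold, then restart at same dose | Agree on stop; conflict on a mandatory restart |
| Grade 2, second episode | Stop, no restart given | Withhold, then half dose | Agree on stop; conflict on restart |
| Grade 2, third episode | Stop, no restart given | Off protocol | No conflict |
| Grade 3 or 4, settled within 10 days | Stop, no restart given | Withhold, may resume at half dose | Agree on stop; differ on a permitted restart |
| Grade 3 or 4, persistent or recurrent | Stop, no restart given | Off study | No conflict |

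**Step 3: is precedence stated?** No. Section 5.2.3 points to 6.6, and 6.11 points to 6.6. Section 6.6 does not refer to 6.5.2, and 6.5.2 does not refer to 6.6.

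**Step 4: how many children?** The documents give only rates for frank events. Assume equal allocation, so 142 / 2 = 71 children on Lovastatin.
- Section 1.7 expects myopathy or marked CPK elevation in fewer than 1 in 500 patients treated for familial hypercholesterolemia: 71 × 1/500 = 0.142, so fewer than about 0.15 cases.
- The rare band in 6.5.2 runs from 1/10,000 to 1/1,000: 71 × 1/10,000 = 0.0071 and 71 × 1/1,000 = 0.071 cases.

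These figures do not count suspected myopathy, which has a lower threshold and is the actual trigger in 6.5.2. Section 6.11 names muscle pain, weakness and tenderness among the most frequent side effects, so suspicion may arise more often than frank disease. The documents give no rate for it.

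**Step 5: the 10-day limit.** Section 5.2.3 applies it to grade 2 or higher. In 6.6 it appears only in the grade 3 or 4 paragraph. Read together, a grade 2 toxicity is withheld until it settles, and a child still at grade 2 or above after more than 10 days off drug leaves the study. The two sections are compatible.

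**The case against.** The strongest reply is that a specific rule for a named condition beside a general rule by grade is an ordinary structure, and that 6.5.2 never says the stop is permanent. Appendix 10, for UK sites, distinguishes temporary interruption from permanent discontinuation, so the authors had the word available. If the stop in 6.5.2 is temporary, 6.6 simply supplies the next step. Conversely, if 6.5.2 is the overriding exception, there is again no clash. Either reading is possible, but the text states neither, and they lead to different restart decisions. Section 6.6 uses withholding where a restart is intended, and 6.5.2 uses a different word with no restart attached. The ambiguity therefore stands.

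Other parts of the reply succeed, and they rule out stronger conclusions that a reader might draw:

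- *That sites would act in opposite ways from the outset.* They would not. For related events of grade 2 or above, both sections stop the drug first.
- *That every muscle event of grade 2 or above is in conflict.* An isolated CPK rise or myalgia conflicts only if myopathy is suspected. Section 6.5.2 lists pain and cramps separately from the weakness it calls myopathy.
- *That grade 3 or 4 is a strict contradiction.* The wording in 6.6 is permissive, so a site that does not resume breaches neither section.
- *That events below grade 2 are in conflict.* Only 6.5.2 speaks there.
- *That the 10-day limit is missing for grade 2.* Section 5.2.3 supplies it, as step 5 of the check shows.
- *That omitting myopathy from 5.2.3 is itself an error.* The toxicity entry there gives examples, and coming off drug is not the same as leaving the study.
- *That section 1.7 shows myopathy to be dose limiting at this trial's dose.* That finding comes from adult cancer patients at 2 to 45 mg/kg/day; the maximum here is 40 mg/day.

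**Conclusion.** The point holds in a narrow form. For a related event that is also suspected myopathy, 6.6 requires a restart after a first or second grade 2 episode and permits one after grade 3 or 4 toxicity that settles within 10 days, while 6.5.2 stops the drug and provides no restart. Nothing says which section prevails.

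This rests on reading the general wording of 6.6 as covering the muscle rows of Appendix 7, which 6.11 supports, and on the absence of any restart in 6.5.2. The number of affected children is expected to be small, with fewer than 0.15 frank cases under the section 1.7 rate and equal allocation; the number of suspected cases cannot be derived. The matter concerns the clarity of a safety rule and the consistency of tolerability data across sites. It does not touch the sample size, the power or the primary analysis method. The 10-day wording is a minor editorial matter only. No view is taken here on which clinical rule is right.

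**What to change.** The sponsor's clinical lead should reconcile 6.5.2 with 6.6 and decide which passage governs suspected myopathy, including whether and how restart is addressed. The decision should be stated once, in 6.6, with cross-references from 6.5.2 and 5.2.3. In the same edit, the grade 2 paragraph of 6.6 should cross-refer to the 10-day criterion in 5.2.3, so that a site reading 6.6 alone finds it.

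The cost is a protocol clarification and a note to sites. It needs no additional data, visits or participants.
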